7.4 INSTITUTIONAL BIOSAFETY COMMITTEE (IBC) REPORTING CRITERIA

7.4.1 Serious Adverse Event Reports to IBC

The Principal Investigator (or delegate) will notify IBC of any unexpected fatal or life-threatening experience associated with the use of PRGN-2009 as soon as possible but in no event later than 7 calendar days of initial receipt of the information. Serious adverse events that are unexpected and associated with the use of the PRGN-2009, but are not fatal or life-threatening, must be reported to the NIH IBC as soon as possible, but not later than 15 calendar days after the investigator's initial receipt of the information. Adverse events may be reported by using the FDA Form 3500a.

7.4.2 Annual Reports to IBC

Within 60 days after the one-year anniversary of the date on which the IBC approved the initial protocol, and after each subsequent anniversary until the trial is completed, the Principal Investigator (or delegate) shall submit the information described below. Alternatively, the IRB continuing review report can be sent to the IBC in lieu of a separate report. Please include the IBC protocol number on the report.

7.4.3 Clinical Trial Information

A brief summary of the status of the trial in progress or completed during the previous year. The summary is required to include the following information:

- the title and purpose of the trial;
- clinical site;
- the Principal Investigator;
- clinical protocol identifiers;

- participant population (such as disease indication and general age group, e.g., adult or pediatric);
- the total number of participants planned for inclusion in the trial; the number entered into the trial to date whose participation in the trial was completed; and the number who dropped out of the trial with a brief description of the reasons;
- the status of the trial, e.g., open to accrual of subjects, closed but data collection ongoing, or fully completed; and
- if the trial has been completed, a brief description of any study results.

7.4.4 Progress Report and Data Analysis

Information obtained during the previous year's clinical and non-clinical investigations, including:

- a narrative or tabular summary showing the most frequent and most serious adverse experiences by body system;
- a summary of all serious adverse events submitted during the past year;
- a summary of serious adverse events that were expected or considered to have causes not associated with the use of the gene transfer product such as disease progression or concurrent medications;
- if any deaths have occurred, the number of participants who died during participation in the investigation and causes of death; and
- a brief description of any information obtained that is pertinent to an understanding of the gene transfer product's actions, including, for example, information about dose-response, information from controlled trials, and information about bioavailability.

7.5 NIH REQUIRED DATA AND SAFETY MONITORING PLAN

7.5.1 Principal Investigator/Research Team

The clinical research team will meet on a regular basis (approximately weekly) when participants are being actively treated on the trial to discuss each participant. Decisions about dose level enrollment and dose escalation if applicable will be made based on the toxicity data from prior participants.

All data will be collected in a timely manner and reviewed by the principal investigator or a lead associate investigator. Events meeting requirements for expedited reporting as described in Section [7.2.1](#) will be submitted within the appropriate timelines.

The principal investigator will review adverse event and response data on each participant to ensure safety and data accuracy. The principal investigator will personally conduct or supervise the investigation and provide appropriate delegation of responsibilities to other members of the research staff.

8 SPONSOR PROTOCOL / SAFETY REPORTING

8.1 DEFINITIONS

8.1.1 Adverse Event

Any untoward medical occurrence in a patient or clinical investigation subject administered a pharmaceutical product and which does not necessarily have a causal relationship with this treatment. An adverse event (AE) can therefore be any unfavorable and unintended sign (including an abnormal laboratory finding), symptom, or disease temporally associated with the use of a medicinal (investigational) product, whether or not related to the medicinal (investigational) product (ICH E6 (R2)).

8.1.2 Serious Adverse Event (SAE)

An adverse event or suspected adverse reaction is considered serious if in the view of the investigator or the sponsor, it results in any of the following:

- Death;
- A life-threatening adverse event (see Section **8.1.3**);
- Inpatient hospitalization or prolongation of existing hospitalization;
 - A hospitalization/admission that is pre-planned (i.e., elective or scheduled surgery arranged prior to the start of the study), a planned hospitalization for pre-existing condition, or a procedure required by the protocol, without a serious deterioration in health, is not considered a serious adverse event.
 - A hospitalization/admission that is solely driven by non-medical reasons (e.g., hospitalization for participant convenience) is not considered a serious adverse event.
 - Emergency room visits or stays in observation units that do not result in admission to the hospital would not be considered a serious adverse event. The reason for seeking medical care should be evaluated for meeting one of the other serious criteria.
- Persistent or significant incapacity or substantial disruption of the ability to conduct normal life functions;
- A congenital anomaly/birth defect;
- Important medical events that may not result in death, be life-threatening, or require hospitalization may be considered a serious adverse drug experience when, based upon appropriate medical judgment, they may jeopardize the patient or subject and may require medical or surgical intervention to prevent one of the outcomes listed in this definition.

8.1.3 Life-threatening

An adverse event or suspected adverse reaction is considered "life-threatening" if, in the view of either the investigator or sponsor, its occurrence places the patient or subject at immediate risk of death. It does not include an adverse event or suspected adverse reaction that, had it occurred in a more severe form, might have caused death (21CFR312.32).

8.1.4 Severity

The severity of each Adverse Event will be assessed utilizing the CTCAE version 5.0.

8.1.5 Relationship to Study Product

All AEs will have their relationship to study product assessed using the terms: related or not related.

- Related – There is a reasonable possibility that the study product caused the adverse event. Reasonable possibility means that there is evidence to suggest a causal relationship between the study product and the adverse event.
- Not Related – There is not a reasonable possibility that the administration of the study product caused the event.

8.1.6 Adverse Events of Special Interest (AESI)

Adverse events of special interest (AESIs) are serious or nonserious AEs that are of clinical interest and should be closely followed.

AESIs include following:

- Infusion-related reactions including immediate hypersensitivity.
- Immune-related adverse events.
- TGF β inhibition mediated skin reactions.
- Anemia.
- Bleeding AEs.

8.2 ASSESSMENT OF SAFETY EVENTS

AE information collected will include event description, date of onset, assessment of severity and relationship to study product and alternate etiology (if not related to study product), date of resolution of the event, seriousness and outcome. The assessment of severity and relationship to the study product will be done only by those with the training and authority to make a diagnosis and listed on the Form FDA 1572 as the site principal investigator or sub-investigator. AEs occurring during the collection and reporting period will be documented appropriately regardless of relationship. AEs will be followed through resolution.

SAEs will be:

- Assessed for severity and relationship to study product and alternate etiology (if not related to study product) by a licensed study physician listed on the Form FDA 1572 as the site principal investigator or sub-investigator.
- Recorded on the appropriate SAE report form, the medical record and captured in the clinical database.
- Followed through resolution by a licensed study physician listed on the Form FDA 1572 as the site principal investigator or sub-investigator.

For timeframe of recording adverse events, please refer to Section **6.1**. All serious adverse events recorded from the time of first investigational product administration must be reported to the sponsor with the exception of any listed in Section **8.4**.

8.3 REPORTING OF SERIOUS ADVERSE EVENTS

Any AE that meets a protocol-defined serious criterion or meets the definition of Adverse Event of Special Interest that require expedited reporting must be submitted immediately (within 24 hours of awareness) to OSRO Safety using the CCR SAE report form. Any exceptions to the expedited reporting requirements are found in Section [8.4](#).

Hospitalizations related to adverse events attributed to disease progression will not need to be reported expeditiously as these events will be captured as a separate study endpoint.

All SAE reporting must include the elements described in Section [8.1.6](#).

SAE reports will be submitted to the Center for Cancer Research (CCR) at:

[contact] and to the CCR PI and study coordinator. CCR SAE report form and instructions can be found at:

<https://ccrod.cancer.gov/confluence/display/CCRCRO/Forms+and+Instructions>

Following the assessment of the SAE by OSRO, other supporting documentation of the event may be requested by the OSRO Safety and should be provided as soon as possible.

In addition, the Sponsor is responsible for reporting adverse events to the FDA in compliance with 21 CFR 312.32. The Sponsor must report all serious, unexpected and related or possibly related adverse events within 15 calendar days after the study team receives knowledge of the event, and all life-threatening and/or fatal unexpected events related or possibly related to the use of the investigational agent within 7 calendar days after the study team receives knowledge of the event.

8.4 WAIVER OF EXPEDITED REPORTING TO CCR

As death/hospitalization due to disease progression is/are part of the study objectives, and captured as an endpoint in this study, they will not be reported in expedited manner to the sponsor. However, if there is evidence suggesting a causal relationship between the study drug and the event, report the event in an expedited manner according to Section [8.3](#)

As M7824 is known to result in immune related toxicities as well as an increased risk of mucosal bleeding as documented in the informed consent and protocol and shared with the FDA, only those SAEs that are unexpected will be reported to the Sponsor in an expedited manner.

The PI will submit a summary table of all grade 3-5 events, whether or not considered related to the product, every 6 months. The report shall include the number of participants treated in the timeframe, the number of events per AE term per grade which occurred in the 6-month timeframe and in total since the start of the study, attribution, and type/category of serious.

Reports will be submitted to the Center for Cancer Research (CCR) at [contact].

The Sponsor might request case summaries for those events if, upon review, the Sponsor determines that an aggregate safety report is required (21CFR312.32(c)(1)(iv)).

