1.1.2 Secondary Objectives

Phase I in participants with recurrent/metastatic HPV positive cancer:

- To assess overall response rate (ORR) according to RECIST 1.1.
- To assess progression-free survival time (PFS).
- To assess overall survival (OS).
- To assess duration of response.
- To assess ratio of participants that are hospitalized because of adverse events attributed to disease progression.

Phase II in participants with newly diagnosed stage I (T1,2 N1)/II/III p16-positive oropharyngeal cancer (OPSCC) cancer:

- To determine if the use of PRGN-2009 alone results in significantly prolonged survival as compared to the expected 80% three-year historical survival for this population.
- To determine the 3-year overall and relapse-free survival rate for PRGN-2009 alone (Arm 2A) as neoadjuvant/ induction therapy before definitive standard of care therapy for this population.
- To assess the safety of the recommended phase II dose (RP2D) of PRGN-2009 (HPV vaccine) alone in this participant population.

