3.3.3 Study Accrual Halting Rules

Accrual will be halted if:

- Phase 1 and Phase 2:
 - There is an occurrence of any death (other than death related to progressive disease or accidental death) that occurs within 30 days of administration of study agents (PRGN-2009 and M7824) for both Phase 1 and Phase 2.
- Phase 2 only:
 - There is a delay in initiation of definitive standard of care therapy of 4 weeks or more beyond the planned start date due to treatment-related toxicities from HPV vaccine in two participants.

- There is occurrence of treatment-related ADRs from HPV vaccine of either Grade 4 (except for laboratory values that are asymptomatic or resolve to Grade ≤ 1 or baseline within 7 days) or of Grade 3 not resolving to Grade ≤ 1 or baseline within 7 days in two participants.

The IRB and the sponsor will be notified if one of the study accrual halting rules has been reached.

The accrual halt will be lifted once the data has been reviewed and there has been a reassessment of available safety information prior to reopening the study to accrual and allowing the study to proceed.

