6. Participants who have completed neoadjuvant or induction immunotherapy on the phase II portion of the protocol will be followed by phone or email for recurrence, adverse events and survival starting 2 months (+/- 2 weeks) after safety visit and then annually (+/- 1 month) until the patient is 5 years out from surgery or completion of chemoradiotherapy.

7. As indicated in Section **12.3**, all subjects will be offered the opportunity to complete an NIH advanced directive form. This should be done preferably at baseline but can be done at any time during the study as long as the capacity to do so is retained. The completion of the form is strongly recommended but is not required.

8. Biochemical profile: Acute care, hepatic and mineral panel as described in Sections **2.2** and **2.4**.

9. In HIV positive participants.

10. Imaging (CT of neck and chest/ MRI, if indicated, for oropharyngeal cancer participants; CT of skull, neck and chest/ MRI, if indicated, for sinonasal SCC; no CT chest required if PET/CT available) at baseline/screening, and at Week 4-5 (CT of neck/ MRI, if indicated, for oropharyngeal cancer participants; CT of skull, neck/ MRI, if indicated, for sinonasal SCC). MRI (with gadolinium) will be used when CT scan is not an option to follow the disease. Bone scans and other imaging assessments may also be performed as clinically indicated. Post-treatment imaging is to be strongly pursued but is not required and may be waived at the discretion of the PI.

11. Where feasible, biopsies will be done at baseline as well as at week 4-5. Biopsies will be done by ENT under direct visualization. Where feasible at least 2 cores will be obtained. If a recent (\leq 6 months preferred) outside biopsy has been performed that specimen may be used in lieu of a baseline biopsy. For patients that have surgery as definitive treatment, Week 4-5 biopsy may be omitted: in this case tumor biospecimens will be obtained from the institution where the patient underwent surgery after the patient signs that institution's release document.

12. Where feasible, research blood (see Section **5.1**) will be collected at baseline, week 3 and week 45 with the following exceptions:

- Samples for AVA analysis will be taken prior to infusion on W1, W3, with research labs on 4-5 or with end of treatment labs if participants come off treatment prior to any of those timepoints.
- Note: Samples may be sent to Precigen, Inc for additional analyses (see Section **5.1.9**).

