12.4.1.1 Risks Associated with Study Drugs

Potential adverse reactions attributable to the administration of the study drug utilized in this trial are discussed in Section [14](#). All care will be taken to minimize side effects, but they can be unpredictable in nature and severity. Participants will be examined and evaluated prior to enrollment. All evaluations to monitor the treatment of participants will be recorded in the medical record. If participants suffer any physical injury as a result of the participation in this study, immediate medical treatment is available at the Clinical Center, National Institutes of Health, Bethesda, Maryland.

Participants may be harmed from being in this study by toxicity due to the drug or combination of drugs given during this study. M7824 is similar to immune check point inhibitors. There are preliminary data to suggest that not all patients benefit from immune check point inhibitors nor M7824. Additionally, there are preliminary data to suggest that an unexpectedly rapid progression of disease occurs in some patients receiving immunotherapy such as immune checkpoint inhibitors.

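### The waiver of expedited reporting for progression-related hospitalization and death rests on endpoint capture that Phase II does not provide before definitive therapy

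*Combined protocol and SAP*

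**What the plan says.** Section 8.2 requires all recorded SAEs to go to the sponsor except those listed in Section 8.4, and Section 8.3 sets the 24-hour limit. Two passages then take progression events out of that route:

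- Section 8.3, on hospitalizations for adverse events attributed to progression: they "will not need to be reported expeditiously as these events will be captured as a separate study endpoint".
- Section 8.4, on death and hospitalization, gives this reason: "As death/hospitalization due to disease progression is/are part of the study objectives, and captured as an endpoint in this study". On that ground it exempts both from the expedited route. Events with evidence of a causal link to study drug stay expedited.

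Neither passage is limited by phase. The endpoint they rely on appears in Section 1.1.2 as "To assess ratio of participants that are hospitalized because of adverse events attributed to disease progression", under the Phase I heading. It recurs in Section 10.1.2.1 (Phase I endpoints) and Section 10.4.3 (Phase I analysis).

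For Phase II, Section 10.1.2.2 lists survival against an 80% three-year historical figure, and three-year overall and relapse-free survival. Section 1.1.2 adds safety of the recommended dose.

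**The concern.** A waiver of this kind is sound when the waived event is the expected course of the disease and is counted elsewhere. Both conditions are met in Phase I, which enrols people with recurrent or metastatic disease. Phase II enrols newly diagnosed people awaiting definitive therapy. A hospitalization or death from progression before that therapy is not a routine outcome there, and Section 12.4.1.11 itself treats delay of potentially curative treatment as a risk.

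If the endpoint behind the waiver does not exist in Phase II, the event is exempt from expedited reporting without the compensating capture. The sponsor then depends, for prompt knowledge, on the study team's judgement that an event was progression and nothing else.

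**Working it through.** The plan states no figure to reproduce. The check traces each waived event to the place where it should be captured.

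**Hospitalization for progression**

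| Place | Phase I | Phase II |
|---|---|---|
| Objectives (1.1.1 to 1.1.3) | Secondary objective | None |
| Endpoints (10.1.1 to 10.1.3) | 10.1.2.1 | None |
| Analysis (10.4.3) | Listed | None |

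The reason given in Sections 8.3 and 8.4 is true for Phase I and untrue for Phase II.

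**Death from progression**

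- Section 10.4.4.3 counts any-cause death from first treatment, which on its face includes Phase II.
- Section 10.3 makes Phase II participants evaluable for overall and relapse-free survival only if they received at least two doses and then definitive therapy.
- Section 10.4.4.1 starts relapse-free survival at completion of chemoradiation.

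A participant who dies of progression before definitive therapy is therefore outside both survival analyses. For death, the reason holds by definition and fails by evaluability in exactly this window.

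**Other prompt routes**

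- The 30-day accrual halting rule (Section 3.3.3) covers deaths "other than death related to progressive disease or accidental death". Its Phase II delay limb counts only delay caused by vaccine toxicity.
- The Clinical Director report of deaths within 30 days (Section 7.3) has the same progression exclusion.

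**Size**

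- Participants affected, from Section 10.2: 20 + 2 = 22 Phase II, of 22 + 20 + 2 = 44 planned evaluable, or 50%.
- Sponsor notice: 24 hours under Section 8.3, against up to six months for the grade 3-5 table in Section 8.4. Six months is about 182.5 days. Against a five-week induction period (5 × 7 = 35 days), 182.5 / 35 = 5.2. Against the 70-day limit from diagnosis to curative treatment in Section 2.1.2.14, 182.5 / 70 = 2.6. A participant's whole pre-definitive window can close before the next table.
- Experience so far: Table 8 gives 0 SAEs in 22 Phase II participants. The exact one-sided 95% upper bound is 1 − 0.05^(1/22) = 12.7%. If the true SAE risk were 5%, the chance of none in 22 would be 0.95^22 = 0.32; at 10% it would be 0.90^22 = 0.10. The record is reassuring but does not exclude a risk of that order.

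**Period in which the ordinary route could apply**

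Section 6.1 records all adverse events from first dose to 28 days after the last. With Phase II doses on Days 1 and 15 (Section 3.2.1), that runs to about Day 15 + 28 = Day 43 if dosing is on schedule. Later, only serious related events need recording, and unrelated events during chemoradiation need not be captured.

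**The case against.** The strongest reply is that the waiver removes one report and leaves most oversight in place. That is correct:

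- The team discusses each participant about weekly, and the principal investigator reviews adverse event and response data (Section 7.5.1).
- SAEs are assessed for relationship by a study physician and entered on the SAE form and in the database (Section 8.2).
- Unexpected serious events associated with the vaccine go to the biosafety committee within 7 or 15 days (Section 7.4.1).
- Events with evidence of causality stay expedited, and grade 3-5 events reach the sponsor every six months whatever their attribution (Section 8.4).
- Sponsor monitoring continues throughout (Section 9), and Section 10.4.7 plans a safety look at the first six Phase II participants.

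A reader might therefore infer too much by saying that these events escape timely review. The documents support only a loss of prompt sponsor notice. The remaining prompt review is largely internal to the study team, or depends on its finding a link to the vaccine.

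A reader might also infer that pre-definitive progression is counted nowhere in Phase II. That is too strong. Section 1.1.3 has an exploratory RECIST response objective with imaging at Week 4-5, so progression can be seen. That capture is partial. Of the scan, the Phase II calendar says: "Post-treatment imaging is to be strongly pursued but is not required and may be waived at the discretion of the PI". A response rate also does not report hospitalization or death.

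Section 12.4.1.1 may look like an acknowledged Phase II hazard where it says that "an unexpectedly rapid progression of disease occurs in some patients receiving immunotherapy such as immune checkpoint inhibitors". That paragraph concerns M7824 and checkpoint inhibitors. Phase II gives the vaccine alone, because Arm 2B closed before enrolment (Section 1.2.9), so it is not evidence of a vaccine risk.

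Finally, one could try to state how many more participants would be treated before the sponsor learned of an event. The documents give no Phase II accrual rate, and Table 8 already lists 22 Phase II participants, equal to the planned 20 + 2. No such number is supportable.

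**Conclusion.** The point holds as an inconsistency with a practical consequence. Sections 8.3 and 8.4 must be reconciled with Sections 1.1.2, 10.1.2, 10.3 and 10.4.3. For hospitalization, the stated basis is absent from Phase II altogether. For death, it is present through overall survival but fails for anyone who does not reach definitive therapy.

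The consequence is confined to events judged to be progression, without evidence of causality, in the Phase II half of the plan (22 of 44). For these, sponsor notice moves from 24 hours to a maximum of six months by the routine table. That is the longest wait rather than the typical one, and a monitoring visit could shorten it.

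This reading assumes that Section 10.3 is applied as written to overall survival, and that the waiver is study-wide because no phase is named. No missed event is shown: Table 8 has no Phase II SAEs. The correction is worth making because the waiver's justification should be true where it is used. The documents do not show that anyone has been harmed by it.

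**What to change.** Limit the progression waiver in Sections 8.3 and 8.4 to Phase I. In Phase II, a hospitalization or death attributed to progression would then follow the ordinary 24-hour SAE route if it occurs before definitive therapy and within the Section 6.1 collection period (first dose to 28 days after the last). The alternative, defining and analysing the hospitalization endpoint in Phase II, would make that part of the rationale true but would not restore prompt notice and would leave the death gap in Section 10.3, so it is second best.

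Add to the Phase II safety table a count of participants who progressed before, or did not receive, planned definitive therapy. Receipt of that therapy must already be known to apply Section 10.3. The count also covers participants whose definitive therapy begins after the collection period ends.

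The 24-hour rule should not be extended through definitive therapy. Section 6.1 does not require unrelated events during chemoradiation to be captured, that care is given at outside institutions (Section 3.1), and contact afterwards is by phone or email, starting about two months after the safety visit and then yearly.

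The cost is a short clause in each of two sections, one table row and, given 0 SAEs in 22 so far, probably few extra expedited reports. Treatment, visits and sample size do not change.
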